6.2 Statistical Analysis

6.2.1 Primary Objectives

The primary objectives of the study are:

1. To assess the effect of DOT Diary on PrEP adherence as measured by TFV-DP in DBS among young MSM initiating PrEP

We will use GEE logistic models to estimate the average effect of assignment to DOT Diary on repeated TFV-DP levels ≥700 fmol/punch, which are consistent with taking 4-7 PrEP doses per week. In exploratory analyses, we will examine whether the between-group difference increases over time. We will also use analogous GEE linear models to estimate the effects of D2 on log-transformed TFV-DP levels, as well as GEE proportional odds models for an ordinal outcome defined as TFV-DP levels consistent with <2, 2-3, and 4-7 doses per week, using cut-points determined by pharmacokinetic benchmarks established through directly-observed dosing.²⁹

Minimum detectable effects (MDEs). We used data from the EPIC study to estimate the baseline level and intraclass correlation (ICC) of the repeated binary measures of DBS TFV-DP levels \geq 700 fmol/punch as 60% and 0.69 respectively, and retention of 80% of participants at 24 weeks. Under these assumptions, we will have 80% power in 2-sided tests with a type-I error rate of 5% to detect average between-group differences in adherence of 23 percentage points.

2. To evaluate the concordance of TFV-DP and FTC-TP in DBS with adherence measured by DOT Diary

Validation of DOT will focus on concordance between aDOT-based assessments of PrEP adherence by the AiCure device with four DBS measurements:

- a. We will use a pharmacokinetic (PK) model with parameters estimated in the DOT-DBS Study (NCT02022657) to calculate the expected TFV-DP levels when each DBS is obtained, based on the aDOT-based pattern of pill-taking over the previous 6 weeks. We will then estimate the correlation between these predictions and observed TFV-DP levels based on DBS, and scatterplot the two measures against each other, with a Lowess smooth. As an additional measure of concordance, we will estimate the proportion of 90% prediction intervals obtained from the PK model that include the measured DBS TFV-DP levels.
- b. We will use aDOT records of pill-taking over the previous 4 and 8 weeks to estimate the average number of PrEP doses per week taken by each participant, then estimate concordance of aDOT- and DBS-based indicators for protective dosing of 4-7 doses/week, with 95% confidence intervals. The DBS indicator will be defined by TFV-DP levels ≥700 fmol/punch. We will also assess concordance of aDOT- and DBS-based measures of <2, 2-3, and 4-7 doses per week, using the Kappa statistic.
- c. We will estimate concordance between an aDOT-based indicator for any PrEP use over the previous 48 hours with an indicator for detection of FTC-TP in DBS, again with 95% confidence intervals.

Margins of sampling error (MSEs). The expected sample of 240 DBS (an average of 3.59 from each of 67 participants, accounting for cumulative 20% loss to follow-up over 24 weeks) will allow us to estimate the concordance of paired binary measures within MSEs of 6.3-8.4 percentage points, depending on the sample concordance. MSEs for concordance of DOT results with detection of FTC-TP will be similar.

3. To assess the acceptability and ease of use of DOT Diary over a 24 week period

Acceptability and ease of use will be measured using the System Usability Scale (SUS) and Client Satisfaction Questionnaire (CSQ-8) adapted for use in the DOT Diary Longitudinal pilot.³⁰ Average values of our measures of acceptability and ease of use will be estimated with 95% confidence intervals.

MSEs. The estimated sample of 54 participants providing end of study data will allow us to estimate mean SUS and CSQ-8 scores within MSEs of 0.27 standard deviations (SDs).

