In 2014, men who have sex with men (MSM) accounted for 70% of new HIV diagnoses in the United States, and MSM are the only US population in which new HIV infections are rising.¹⁰ Black and Latino men are at particularly high risk, with HIV infection rates estimated to be 6.6 and 2.9 fold higher than among White men. Disparities in HIV prevalence increased in 2008-2011, and grew fastest in the youngest age groups.¹¹ Young MSM (YMSM) accounted for nearly 20% of the estimated HIV diagnoses nationwide and over 80% of new HIV infections among youth in 2014. Furthermore, Black and Latino YMSM accounting for 55% and 33% of HIV infections among YMSM, respectively.¹⁰ Despite the promise of PrEP in preventing HIV acquisition among YMSM, PrEP uptake has been low in this vulnerable population. According to national prescription data, youth under 24 are the least likely to initiate PrEP, with only 9% of PrEP initiations in 2015 occurring in this age group.¹² In a recent national survey, only half of YMSM aged 15-24 had heard of PrEP, and 1.7% had ever used PrEP.¹³ Demonstration projects also highlight challenges with PrEP uptake and adherence. In the US Demo Project of 550 MSM, only 20% were age 25 or under, and PrEP uptake was lower among younger, non-white. and less educated persons.¹⁴ In multivariate analysis, the only independent predictors of adherence as measured by tenofovir diphosphate levels in dried blood spots were Black race (adjusted odds ratio, aOR 0.28, 95% CI 0.12-0.64) and enrollment in Miami (aOR 0.32, 95% CI 0.17-0.60).¹⁵ Self-reported adherence, pill counts, and medication possession ratios did not completely explain the disparities in TFV-DP levels. Similar findings were seen in the ATN 110 study of YMSM aged 18-22, where PrEP uptake was only 16%, and PrEP adherence was lower among Black YMSM and declined overall during follow-up, particularly with less frequent visits.¹⁶ Clearly, future PrEP studies must include sizeable numbers of African American, Latino, and young MSM, who are at high risk for HIV and may require timely adherence support, triggered by an accurate measure of adherence. Additionally, studies of on-demand (or 2-1-1) PrEP, in which 2 doses of TDF/FTC PrEP are taken in the 24 hours prior to sex, and 1 dose each taken 24 and 48 hours later, have demonstrated promise in a randomized study[refs] and

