5.6.2 Enrollment visit

Participants who are eligible after screening will return to the clinic for an enrollment visit. All screening procedures must be complete within 4 weeks (28 days) of the enrollment visit. At the enrollment visit, HIV testing will be performed according to HIV testing algorithm in SSP. Participants will complete an online questionnaire via computer-assisted self-interview (CASI) that gathers data on baseline demographics, drug use and sexual behaviors, knowledge and use of PrEP, and experience using technology. Participants will also be provided risk reduction counseling, condoms, and lubricant. A study clinician will then perform a medical history and limited physical exam (this may be done at screening and updated at enrollment, based on site preference). Study staff will confirm participant eligibility and enroll the participant into the study.

Participants will then be randomized to receive the DOT Diary intervention immediately at enrollment (intervention arm) or PrEP alone (control arm) in a 2:1 ratio (see randomization procedures in Section 5.3). Participants who are randomized will be considered enrolled in the study. Participants in the intervention arm will be provided instructions to download the app on to their smartphone. Study staff will demonstrate how to use the DOT Diary app, and participants will complete the tutorial in the app and demonstrate taking their first dose of TDF/FTC using the app. Participants will also select a daily dosing time, and the app will be programmed to send the participant a daily text message or app notification at this time to take their pill and use the app. Participants will also set preferences regarding the sexual diary, including preferences regarding partner rating items. Staff will instruct participants to not include any personally identifiable information about partners in the sexual diary, such as real names or contact information. Staff will emphasize that partner nicknames should be used that help the participant identify the partner but are not easily identifiable to anyone else. For example, "Bob" or "Leather pants guy."

All participants will be dispensed 3 bottles of TDF/FTC (90 pills) and provided the PrEP Basics handout and adherence counseling regarding importance of daily adherence to PrEP for maximal protection and strategies to integrate pill-taking into one's routine. The participant will be provided a stipend for completion of the enrollment visit.

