Study personnel will have access to real-time data on a browser-based dashboard. Study personnel may switch on automated notifications (notifications are based on adherence thresholds) and will receive regular participant and site updates (dosing and intervention summaries, site performance data, and week on week adherence rates). In addition to dosing data, the platform will automatically flag behavioral events for further review that may be indicative of a participant intentionally not taking the medication, or 'feigning' adherence. If deceptive behavior is confirmed by human review, study personnel are notified. Based on the data, study staff will determine whether to follow up with a participant and select a method for intervention. If the intervention is conducted via the browser-based dashboard (by phone, SMS text, or request for in-clinic visit), the intervention will be logged. Intervention will consist of non-judgmental contact with the participant, such as asking if they are having trouble using the mobile app or taking their medication as directed. At the end of the study, all raw data logged on the AiCure platform will be distributed to study personnel for analysis.

On the participant side, after dosing is completed, video data are encrypted and transmitted to a secure centralized location for further analysis. Once received at the

centralized location, the data are then removed from the device (store and forward). The captured data and video are reviewable through a roles and rules restricted system ensuring privacy of the information, allowing access to the data by study team members at the research sites. Video data captured by the aDOT platform will only be available to AiCure personnel and will be analyzed for proper medication administration. Individuals outside the clinical sites will not know the identity of the study participants and will be destroyed on or before January 1, 2021. The system is compliant with the Health Insurance Portability and Accountability Act (HIPAA), which protects the privacy and security of healthcare information.

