8.2 Dried Blood Spots (DBS)

Dried blood spot (DBS) specimens will be collected at the week 6, 12, 18, and 24 visits. Specimens will be frozen and batch shipped to the University of Colorado Pharmacology Laboratory for testing of TDF-DP and FTC-TP drug concentrations.

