To evaluate the concordance of TFV-DP and FTC-TP in DBS with adherence measured by DOT Diary. Validation of DOT will focus on concordance between aDOT-based assessments of PrEP adherence by the AiCure device with four DBS measurements. *First*, we will use a pharmacokinetic (PK) model with parameters estimated in the DOT-DBS Study (NCT02022657) to calculate the expected TFV-DP levels when each DBS is obtained, based on the aDOT-confirmed pattern of pill-taking over the previous 6 weeks, as assessed using aDOT-confirmed results. In sensitivity analyses, we will include self-reported pill-taking. We will then estimate the correlation between these predictions and observed TFV-DP levels based on DBS, and scatterplot the two measures against each other, with a Lowess smooth. As an additional measure of concordance, we will estimate the proportion of 90% prediction intervals obtained from the PK model that include the measured DBS TFV-DP levels. **Second**, we will also use aDOT-confirmed aDOT records of pill-taking over the previous 4 and 8 weeks to estimate the average number of PrEP doses per week taken by each participant, then estimate concordance of aDOT- and DBS-based indicators for protective dosing of 4-7 doses/week, with 95% confidence intervals. The DBS indicator will be defined by TFV-DP levels ≥700 fmol/punch. We will also assess concordance of aDOT- and DBSbased measures of <2, 2-3, and 4-7 doses per week, using the Kappa statistic. Third, we will estimate concordance between an aDOT-based indicator for any PrEP use over the previous 48 hours with an indicator for detection of FTC-TP in DBS, again with 95% confidence intervals. Margins of sampling error (MSEs). The expected sample of 240 DBS (an average of 3.59 from each of 67 participants, accounting for cumulative 20% loss to follow-up over 24 weeks) will allow us to estimate the concordance of paired binary measures within MSEs of 6.3-8.4 percentage points, depending on the sample concordance. MSEs for concordance of DOT results with detection of FTC-TP will be similar.

To assess the acceptability and ease of use of DOT Diary over a 24 week period.

Acceptability and ease of use will be measured using the System Usability Scale (SUS) and

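### The PK prediction at each DBS should use the full aDOT dosing record since enrolment, not only the last six weeks

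*Protocol*

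**What the plan says.** Protocol 6.2.1, objective 2, item a will use an external PK model to "calculate the expected TFV-DP levels when each DBS is obtained, based on the aDOT-based pattern of pill-taking over the previous 6 weeks". The SAP (Primary Objectives, concordance objective, first analysis) keeps the window and specifies confirmed doses: "based on the aDOT-confirmed pattern of pill-taking over the previous 6 weeks, as assessed using aDOT-confirmed results". Its one sensitivity analysis for this step adds self-reported doses and does not lengthen the window. The outputs are a correlation, a scatterplot with a Lowess smooth, and the share of 90% prediction intervals that contain the measured level.

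The sampling times are fixed in Protocol 8.2: "Dried blood spot (DBS) specimens will be collected at the week 6, 12, 18, and 24 visits". Intervention participants start with the app at enrolment, where they "demonstrate taking their first dose of TDF/FTC using the app" (Protocol 5.6.2). Protocol 6.1 adds: "At the end of the study, all raw data logged on the AiCure platform will be distributed to study personnel for analysis". Protocol 4.2 excludes anyone who used PrEP in the preceding 4 months.

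Neither document gives a starting level for the model, carries its state forward from the last visit, seeds it from the previous DBS, or explains why six weeks is enough.

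**The concern.** At week 6 the six-week window is the participant's whole history. At weeks 12, 18 and 24 it discards doses that the app recorded and that may still contribute to the measured level. With no starting level, predictions at those three visits can only be too low, while those at week 6 are not, so the pooled analysis mixes predictions made on different scales.

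The statistic most exposed is coverage of the 90% prediction intervals. A low figure would look like failure of the app to capture ingestion when it came from the window.

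Nor is the shortfall a common factor that cancels across participants. It grows when recent dosing is lower than earlier dosing, and the Background reports that pattern in a cited study of young MSM: "PrEP adherence was lower among Black YMSM and declined overall during follow-up, particularly with less frequent visits".

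**Working it through.** **The plan's own figures.** With full retention at week 6 and geometric loss to 80% at week 24, DBS per visit are 67 × 0.8^(k/3), k = 0 to 3: 67.0, 62.2, 57.7 and 53.6. The total is 240.5, or 3.59 per participant, as stated. Weeks 12-24 contribute 173.5 (72%). The margin 1.96 × √[p(1−p)(1 + 2.59 × 0.69)/240.5] is 6.3 points at p = 0.9 and 8.4 at p = 0.8, matching the stated range. This takes the ICC of 0.69 from objective 1.

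**Days omitted.** 7 × week − 42 gives 0, 42, 84 and 126 days at weeks 6, 12, 18 and 24, or 0%, 50%, 67% and 75% of the record.

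**Assumptions.** The documents give neither a half-life nor a prediction SD. I assume first-order loss, a half-life h of 10 to 25 days, a zero level at the start of the window, and log-normal prediction error with SD s of 0.2, 0.3 or 0.5.

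**Shortfall under steady dosing.** At day T the omitted share is 1 − (1 − 2^(−42/h))/(1 − 2^(−T/h)). For h = 21 at week 12: 1 − 0.75/0.9375 = 20.0%.

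**Coverage.** With d = −ln(1 − share), coverage at a visit is Φ((1.645s − d)/s) − Φ((−1.645s − d)/s), pooled with the DBS counts as weights. For h = 21 and s = 0.3 the four visits give 90.0, 80.8, 76.5 and 75.3%, and the pooled value is 81.1%.

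| Half-life (days) | Shortfall, weeks 12 / 18 / 24 (%) | Pooled coverage, s = 0.2 (%) | s = 0.3 (%) | s = 0.5 (%) |
|---|---|---|---|---|
| 10 | 5.2 / 5.4 / 5.4 | 89 | 90 | 90 |
| 14 | 11.1 / 12.3 / 12.5 | 85 | 88 | 89 |
| 17 | 15.3 / 17.6 / 18.0 | 80 | 85 | 88 |
| 21 | 20.0 / 23.8 / 24.7 | 71 | 81 | 87 |
| 25 | 23.8 / 29.1 / 30.5 | 62 | 76 | 85 |

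**Changing adherence.** Let q = 2^(−42/h). For a doses per week to week 18 and b afterwards, the week-24 shortfall is a(1 − 2^(−126/h))q / [a(1 − 2^(−126/h))q + b(1 − q)]. Over h = 10, 14, 17, 21 and 25:
- 7 then 2 doses per week: 17, 33, 43, 54 and 61%
- 2 then 7 doses per week: 1.6, 3.9, 5.9, 8.6 and 11%

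Suppose 30% of participants have rates of 1, 0.75, 0.5 and 0.25 times their starting rate over the four periods and the rest are steady. The omitted share for a decliner in period k is 1 − m_k/Σ m_j q^(k−j), summed over j = 1 to k. Pooled coverage at s = 0.3 is then 89, 87, 83, 77 and 71%.

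**Correlation.** A simulation used 60,000 participants, dosing fractions uniform on 0.2-1.0, s = 0.3, the same 30% decliners and the retention above. Pooled Pearson r, full record against six-week window, was 0.809/0.807, 0.804/0.795, 0.804/0.784, 0.803/0.766 and 0.805/0.748. The fall is at most about 0.06.

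**The case against.** **The text is silent on the initial condition.** Six weeks is also the visit interval, so the phrase could mean dosing since the last visit with the model state carried forward. That would be sound, but an analyst cannot learn it from either document. If the state were instead seeded from the previous DBS, predictions would depend partly on an earlier measurement and would have no seed after a missed visit. If each window were treated as steady state, the later visits would be nearly right but week 6 would be over-predicted by 1/(1 − 2^(−42/h)) − 1, about 6% at a 10-day half-life and 45% at 25 days. So the direction of error depends on the start chosen. The full record with a zero start removes the error in either case.

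**Materiality is uncertain.** This stands. In 10 of the 15 coverage cells the loss is no more than 5.1 points, inside the plan's best margin of 6.3. Large losses need a long half-life together with a small SD. The correlation, the first output named, barely changes.

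**Falling adherence is the unfavourable direction.** This also stands. Rising dosing gives a shortfall of only about 2-11%, and the cited decline was steepest with less frequent visits, whereas visits here stay six-weekly.

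**Week 6 escapes only on the nominal schedule.** True. A week-6 visit seven days late would lose 1 − (1 − 2^(−42/h))/(1 − 2^(−49/h)), about 2-7% of the predicted level over the same half-lives.

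**Conclusion.** The concern holds. Both documents restrict the model input to six weeks, the complete record is available, and nothing in the text supplies what the window leaves out. With a zero level at the start of each window, the three later visits are under-predicted. The effect is negligible at a half-life of 10 days and becomes substantial for interval coverage only when the half-life is long and the prediction SD small. These sizes rest on assumed values of both, on first-order loss and on nominal visit dates.

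The analysis is descriptive, within a pilot, and the randomized comparison is not affected. The change is still worth making: it protects the first validation analysis of a primary objective and costs nothing if the half-life turns out to be short.

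**What to change.** In Protocol 6.2.1 item 2a and in the first concordance analysis of the SAP, including its self-report sensitivity analysis, replace the six-week limit with the full aDOT dosing record from the enrolment dose to the date of each DBS, and state a starting level of zero at enrolment. The 4-month PrEP exclusion makes that start reasonable. If carrying the model forward or seeding it from the previous DBS is what was meant, say so, and say what happens after a missed visit.

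The cost is one phrase in each document. No new data are needed and every DBS stays in the analysis.

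A minor clarification can be made at the same time, though the verdict does not rest on it. Item 2b says: "We will use aDOT records of pill-taking over the previous 4 and 8 weeks to estimate the average number of PrEP doses per week". At week 6 only six weeks of record exist, and no divisor is given for the 8-week average. Either average over the shorter of 8 weeks and time since first dose, which keeps all 240 DBS, or leave week 6 out of the 8-week analysis. Leaving it out gives 173.5 DBS and widens the margins from 6.3-8.4 points to about 6.5-8.6 (67 participants) or 6.7-8.9 (the 62 expected at week 12). The documents do not show whether the present wording biases week-6 concordance.

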6.2.2 Secondary Objectives

The secondary objectives of the protocol are:

1. To assess PrEP coverage of sexual acts (prevention-effectiveness adherence) as measured by DOT Diary

We will estimate the probability of coverage of condomless receptive sexual acts in each period, with sexual acts treated as trials, and coverage as success. Confidence intervals will be obtained using GEE binomial models, with robust standard errors will be used to account for within-subject correlation as well as over-dispersion of the binomial outcome.

MSEs. We also used EPIC data to estimate the average number of condomless receptive sexual acts per participant as ~7. Under this assumption, we will be able to estimate coverage probabilities within MSEs of 4-10 percentage points, depending on coverage levels and the ICC of coverage across episodes.

2. To evaluate the daily use of the DOT and diary components of DOT Diary through 24 weeks of follow-up

We will estimate the average use of DOT and the diary, as proportions of days and weeks on study, respectively.

MSEs. Proportions will be estimated within MSEs of 7-12 percentage points, depending on the sample proportions.

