DOT Diary Longitudinal Pilot Statistical Analysis Plan

NCT03771638

PI: [name] Date: April 5, 2019

Statistical Analysis Plan

Primary Objectives

To assess the effect of DOT Diary on PrEP adherence as measured by TFV-DP in DBS among young MSM initiating PrEP. We will use GEE logistic models to estimate the average effect of assignment to DOT Diary on repeated TFV-DP levels ≥700 fmol/punch, which are consistent with taking 4-7 PrEP doses per week. In exploratory analyses, we will examine whether the between-group difference increases over time. We will also use analogous GEE linear models to estimate the effects of D2 on log-transformed TFV-DP levels, as well as GEE proportional odds models for an ordinal outcome defined as TFV-DP levels consistent with <2, 2-3, and 4-7 doses per week, using cut-points determined by pharmacokinetic benchmarks established through directly-observed dosing.²⁸ To help with interpretation of these results, retention in the study will at each 6-week visit will be reported. Minimum detectable effects (MDEs). We used data from the EPIC study to estimate the baseline level and intraclass correlation (ICC) of the repeated binary measures of DBS TFV-DP levels ≥700 fmol/punch as 60% and 0.69 respectively, and retention of 80% of participants at 24 weeks. Under these assumptions, we will have 80% power in 2-sided tests with a type-I error rate of 5% to detect average between-group differences in adherence of 23 percentage points.

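### Is the 6.3-8.4 point margin for aDOT-DBS concordance overstated because it covers only concordance of 80% or more?

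*Protocol*

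**What the plan says.** Protocol section 6.2.1, objective 2, compares app-based (aDOT) and DBS-based indicators of adherence. For the binary comparison the analysts will "then estimate concordance of aDOT- and DBS-based indicators for protective dosing of 4-7 doses/week, with 95% confidence intervals". The planning basis is "The expected sample of 240 DBS", described as "an average of 3.59 from each of 67 participants", "accounting for cumulative 20% loss to follow-up over 24 weeks". From this the protocol concludes that the sample "will allow us to estimate the concordance of paired binary measures within MSEs of 6.3-8.4 percentage points, depending on the sample concordance". The SAP, under Primary Objectives, repeats the claim: "within MSEs of 6.3-8.4 percentage points, depending on the sample concordance". Both documents add that the margin for agreement with FTC-TP detection will be similar.

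An ICC appears only under objective 1, for the repeated indicator of TFV-DP at or above 700 fmol/punch. There the EPIC-based inputs are "fmol/punch as 60% and 0.69 respectively, and retention of 80% of participants at 24 weeks" (SAP, Primary Objectives; the same values are in protocol 6.2.1). No ICC is given for agreement, and no expected level of agreement is stated.

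For daily use of the app, protocol section 6.2.2 says "Proportions will be estimated within MSEs of 7-12 percentage points, depending on the sample proportions".

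**The concern.** The margin of a proportion is widest at 50% and narrows towards 100%. A range qualified only by the sample concordance, with no limits on that concordance, invites the reader to treat its upper end as the widest margin possible. Worked back, however, 8.4 points belongs to 80% concordance, and with the same inputs lower agreement gives wider margins. The app-use range adds to the impression. It has almost the same wording but reproduces as a range from 90% down to 50%, so it does include the worst case.

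Concordance is a primary objective, and the pilot is meant to prepare a larger efficacy trial. If the planned precision were really overstated, a reader would expect more from the validation result than 67 participants can give.

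**Working it through.** **Inputs**

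- 240 DBS, 67 intervention participants, 3.59 DBS each: protocol 6.2.1, objective 2. The 3.59 already allows for the 20% loss: 1 + 0.8^(1/3) + 0.8^(2/3) + 0.8 = 3.59, taking no loss before week 6.
- 95% two-sided interval, z = 1.96: the plan's 95% confidence intervals.
- ICC 0.69: stated for the TFV-DP indicator under objective 1. Its use for agreement is inferred here.
- Concordance p: not given, so it is varied.

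**Formula**

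Margin = 1.96 × sqrt(p(1 − p) × DE / N), with design effect DE = 1 + (3.59 − 1) × ICC.

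**Reproducing the stated range**

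DE = 1 + 2.59 × 0.69 = 2.787, and 240 / 2.787 = 86.1 effective samples.

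- p = 0.90: 1.96 × sqrt(0.09 / 86.1) = 6.34 points
- p = 0.80: 1.96 × sqrt(0.16 / 86.1) = 8.45 points

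With the unrounded 67 × 3.59 = 240.5 samples these become 6.33 and 8.44, which match 6.3 and 8.4. The ratio of the limits agrees too: (8.4 / 6.3)² = 1.78 and 0.16 / 0.09 = 1.78.

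**Could other inputs give the same range?**

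- ICC = 0: the largest possible margin, at 50%, is 6.3 points, so 8.4 is never reached. The stated range must therefore allow for repeated samples within a person.
- ICC of about 0.29: 8.4 is the margin at 50%, but 6.3 then falls at about 83%, an unlikely planning value.
- Of the combinations tried, only ICC 0.69 with 80% and 90% fits both ends at round values.

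**Margins outside 80-90% (ICC 0.69, N = 240)**

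| Concordance | 95% | 90% | 85% | 80% | 75% | 70% | 60% | 50% |
|---|---|---|---|---|---|---|---|---|
| Margin (points) | 4.6 | 6.3 | 7.5 | 8.4 | 9.1 | 9.7 | 10.3 | 10.6 |

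The largest excess over the stated upper limit is 10.6 − 8.4 = 2.2 points. Above 90% the margin is better than stated.

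**Sensitivity to the unstated ICC for agreement**

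| ICC | at 70% | at 50% |
|---|---|---|
| 0 | 5.8 | 6.3 |
| 0.3 | 7.7 | 8.4 |
| 0.5 | 8.8 | 9.6 |
| 0.69 | 9.7 | 10.6 |

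With an ICC of about 0.29 or less, 8.4 points covers every level of concordance.

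**The app-use range for comparison (n = 67, one value per person)**

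- p = 0.90: 1.96 × sqrt(0.09 / 67) = 7.2
- p = 0.50: 1.96 × sqrt(0.25 / 67) = 12.0

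These match the stated 7-12 points.

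**The case for a change.** The best argument for changing the text is that concordance below 80% is quite possible. The SAP's main comparison counts aDOT-confirmed doses and brings in self-reported pill-taking only in sensitivity analyses. A pill taken without the app raises TFV-DP but is not counted as a confirmed dose. Agreement cannot exceed 1 minus the gap between the two marginal rates. Suppose 83% reach 700 fmol/punch (60% plus the 23-point detectable difference) and 50% are aDOT-confirmed at four or more doses per week. Concordance is then at most 1 − 0.33 = 67%, with a margin of 1.96 × sqrt(0.67 × 0.33 / 86.1) = 9.9 points. Low agreement is also where a reader would most want to know the precision.

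The bound is valid, and it shows that values under 80% cannot be ruled out. It does not show that they are expected. The 83% adds a detectable effect to an outside estimate, and the plan does not present it as a forecast. The 50% is an assumption. It cannot be borrowed from the app-use margin, which concerns average days and weeks of use rather than the share of DBS intervals with four or more confirmed doses per week. Nor must two different quantities be planned over the same range.

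What stands is a gap in reporting: the range and the ICC are not written down, and the FTC-TP margin is called similar without its own assumptions.

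**Conclusion.** The concern does not call for a change. The range is arithmetically right for concordance of 90% to 80% under ICC 0.69, and the sentence says that the margin depends on the concordance found. Two planning assumptions are left unstated, but a statistician can recover them from figures in the same section.

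The most at stake is 2.2 points, or 25% of the stated upper limit (10.56 against 8.45). That needs both 50% agreement and an ICC for agreement as high as the one for TFV-DP. At 70% concordance the excess is 1.3 points with ICC 0.69 and 0.4 with ICC 0.5. At 80% or more with ICC 0.69, or at any concordance with an ICC of about 0.29 or less, there is none.

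Nothing downstream would move. The trial enrols up to 100 participants whatever this margin is, and no success threshold or decision rule refers to it. The reported precision will come from 95% confidence intervals at the concordance actually observed. Writing in the 80-90% range and the ICC would help a reader of the planning section, but it would leave the analysis, the results and the conclusions as they are.
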